### Thrombocytopenia

- Pre-treatment hematologic parameters prior to administration of chemotherapy will include an ANC greater than or equal to  $1.5 \times 10^9/L$ , platelet greater than or equal to  $100,000 \text{ mm}^3$

#### **Dose Modification for Thrombocytopenia**

Nadir of last course ≤ 100,000	Dose of Cisplatin Platelets (day 1 of each cycle)	
	<100,000	≥100,000
≥ 50,000	Hold	Cisplatin = 100%
< 50,000 (1 st occurrence)	Hold	Cisplatin = 80%
<50,000 (2 nd occurrence)	Hold	Cisplatin = 60%

\*\* Please note that dose reduction percentage is calculated by taking off from the original dose and not the previous dose.

#### **Dose Modification of Cisplatin in Kidney Impairment**

Calculated Creatinine Clearance (mL/min)	Percent Dose to Give	
≥ 60	100%	
< 60	0% (withhold treatment for a maximum of 2 weeks and repeat serum creatinine weekly after additional hydration), then	
	If CCI was < 60 mL/min and is now:	** The percent dose to give is:
	> 50 but < 60	80%
	≥ 40 but ≤ 50	50%
	< 40	0%

\*\*Please note that dose reduction percentage is calculated by taking off from the original dose and not the previous dose.

If creatinine clearance recovers, the dose of Cisplatin for the following cycle should be re-escalated to the previous dose level.

Formula to calculate Creatinine Clearance:

$$\text{CrCl (mL/min)} = \frac{(140-\text{age}) (\text{weight kg})}{\text{_____}}$$

CONFIDENTIAL

This document is confidential. Do not disclose or use except as authorized.

$72 \times \text{serum creatinine (mg/dL)}$

N.B. For females, use 85% of calculated CrCl value.

### Ototoxicity, Nausea and Vomiting

Cisplatin is the preferred therapy for TPF and chemoradiotherapy, Carboplatin may be substituted for Cisplatin if a patient develops grade 3 ototoxicity, or an unacceptable Cisplatin associated nausea and vomiting, after receiving 1 or 2 doses of Cisplatin.

Dose alteration for toxicity is to be based on single worst toxicity. Once Carboplatin dose is reduced, there will be no re-escalation.

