### 7.2 Dose Modifications/Delays

#### 7.2.1 Cisplatin

##### Peripheral Neuropathy

- A neurological examination must be performed at least before entry into the study and then **Should be done at the end of CRT for chemoRT groups and then at 3 month follow up.** In case of symptoms or signs experienced by the patient, more frequent examinations should be performed and dose modification will be as follows:
  - Grade 0, 1: No change
  - Grade  $\geq 2$ : Carboplatin at an AUC of 2 may be substituted for Cisplatin

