##### Ototoxicity

- Cisplatin is known to cause high frequency hearing loss. If grade 1 or 2 hearing loss occurs, the risk of additional hearing loss versus the potential benefit of continuing Cisplatin chemotherapy should be made. Grade 3 and 4 hearing loss is an indication to discontinue the drug however this decision can be made with the patient and after formal hearing tests.
- Audiometric testing will be performed at baseline and prior to each dose

CONFIDENTIAL

This document is confidential. Do not disclose or use except as authorized.

- In case of grade 3 or 4 toxicity, Carboplatin (at dosage of AUC 2) may be used to replace Cisplatin in the remaining chemo cycles. The dose of Carboplatin AUC 2 will be calculated based on the Calvert formula.

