### Neurotoxicity

- In the event of neurotoxicity ( $\geq$  grade 3), Carboplatin therapy is discontinued.

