## 10.0 STUDY CALENDAR (History, Exam and Lab)

	Pre-Study 	Post Surgery Surveillance Follow up	During Chemo/RT, groups 2,3	Post CRT Follow up (± 1 month)
Informed Consent	To be obtained before enrollment			
Medical History	Within 10 days before registration	Every Visit	Per SOC at all clinical visits	Every Visit
Smoking History	Within 10 days before registration			
Concurrent meds	At Screening	Every Visit	Weekly	
Physical Exam^1	Within 10 days before registration	Every Visit	Per SOC at all clinical visits	
CBC/BMP	Within 10 days before registration	Preop and post-op and then no requirement for Groups I and II and per SOC for Group IIIA and IIIB	Preop and post-op and then no requirement for Groups I and II and per SOC for Group IIIA and IIIB	
Dysphagia Assessment Questionnaire	Within 10 days before registration	12, 24, 36 months (± 1 month)	Weekly	12, 24, 36 months
Adverse Event evaluation			Weekly	Each visit
B-HC (for WOCP)	Within 7 days before registration			

 Ht, Wt, Performance status, neurologic examination, vital signs (heart/blood pressure/temperature). Height is only collected at baseline/pre-study.

CONFIDENTIAL

This document is confidential. Do not disclose or use except as authorized.

Tumor Assessment						
	Pre-Study	Surgery	Pathological Evaluation	ChemoRT (if reassigned)	Reassessment (Week 8-10)	Surveillance ( $\pm$ 1 month)
Physical tumor Examination	Patients get an exam as part of their routine visits, same for TNM and will be done when the patient is seen and before they are consented	Intraoperative	Path Check List		X	
TNM Staging	patients get an exam as part of their routine visits, same for TNM and will be done when the patient is seen and before they are consented		Path Check List			
Nasopharyngoscopy					X	
Examination under anesthesia (EUA)	Within 8 weeks before registration if possible. (Does not need to be repeated if time period exceeds 8 weeks)	May be done if investigator deems it necessary				
PET/CT and/or high resolution CT or MRI of the neck (base of skull clavicles)	Within 28 days before registration			PET/CT or CT with contrast and examination At 12-16 weeks	PET/CT or CT with contrast and examination Refer to Section 5.0 "Treatment Plan" for the frequency in each group	

CONFIDENTIAL

This document is confidential. Do not disclose or use except as authorized.

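### Section 7.2.1 gives inconsistent conditions for switching from cisplatin to carboplatin, and the audiometry it requires is missing from the study calendars

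*Combined protocol and SAP*

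**What the plan says.** All of this is in the combined protocol and SAP.

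- **Peripheral neuropathy (7.2.1).** Grades 0 and 1 need no change. At grade 2 or above, "Carboplatin at an AUC of 2 may be substituted for Cisplatin". No upper grade is given.
- **Neurotoxicity (later in 7.2.1).** At grade 3 or above, "Carboplatin therapy is discontinued".
- **Ototoxicity (7.2.1).** "Grade 3 and 4 hearing loss is an indication to discontinue the drug however this decision can be made with the patient", after formal hearing tests. At grade 3 or 4, carboplatin at AUC 2 "may be used to replace Cisplatin in the remaining chemo cycles". There is no condition on how many cisplatin doses have been given.
- **Ototoxicity, Nausea and Vomiting (7.2.1).** This paragraph says it covers both TPF and chemoradiotherapy. It permits substitution for grade 3 ototoxicity or unacceptable cisplatin-related nausea and vomiting, and closes with the words "after receiving 1 or 2 doses of Cisplatin". Grade 4 is not mentioned.
- **Testing (7.2.1, Ototoxicity).** "Audiometric testing will be performed at baseline and prior to each dose".
- **Section 10 calendars.** Neither the study calendar nor the correlative studies calendar has an audiometry row. A footnote to the study calendar does list a neurologic examination. For blood counts and chemistry the entry is "Preop and post-op and then no requirement for Groups I and II and per SOC for Group IIIA and IIIB".

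**The concern.** A dose-modification section should lead two readers with the same patient to the same set of permitted actions. Here the answer can depend on which paragraph is read. That matters for two reasons.

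First, it affects what patients in Groups IIIA and IIIB receive. It also reaches salvage treatment, because Section 5.2 carries the same cisplatin regimen into salvage chemoradiotherapy. More than one team must interpret the text: Appendix 4 has the participating site deliver chemoradiotherapy under the same rules.

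Second, it affects what is measured. Section 7.1.1 lists nausea and vomiting, peripheral neuropathy and ototoxicity among the major dose-limiting toxicities of cisplatin. Section 16.5 makes toxicity a secondary endpoint, reported as a rate per arm with exact binomial 90% intervals. If scheduled audiograms are missed because the calendar omits them, hearing loss without symptoms could go uncounted, and the grade that triggers the hearing rule could go unrecognised.

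**Working it through.** The plan gives no figure to reproduce on this point. The check sets the paragraphs side by side, with one short calculation to put the dose clause in scale.

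**Neuropathy.** This assumes that neurotoxicity, which the protocol does not define, includes peripheral neuropathy.

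| Grade | Peripheral Neuropathy paragraph | Neurotoxicity paragraph | Result |
|---|---|---|---|
| 2 | switch to carboplatin permitted | not triggered | consistent |
| 3 or more | switch to carboplatin permitted | carboplatin stopped | conflict |

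The Neurotoxicity paragraph does not say that the toxicity must have arisen or worsened on carboplatin. A patient first graded at 3 on cisplatin, switched under one rule and still at grade 3, therefore already meets the other rule.

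**Hearing.**

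| Case | Ototoxicity paragraph | Ototoxicity, Nausea and Vomiting paragraph | Result |
|---|---|---|---|
| Grade 3 after dose 1 or 2 | permitted | permitted | agree |
| Grade 3 after dose 3 or later | permitted if cycles remain | not provided for, if the dose clause applies to hearing | differ |
| Grade 4 | permitted if cycles remain | silent | differ |

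The dose clause follows a comma after nausea and vomiting. It can be read as limiting only that trigger, or both triggers.

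**Scale of the dose clause under weekly dosing.** Inputs: cisplatin weekly (Section 5.1); radiotherapy 5 days a week; 50 Gy at 2.0 Gy per fraction for Group IIIA and 56 Gy at 2.0 Gy for the higher-dose volume in Group IIIB (Target Dose Prescriptions). The protocol states no number of cisplatin doses, so one per radiotherapy week is assumed.

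- Fractions = total dose / dose per fraction. IIIA: 50 / 2.0 = 25. IIIB: 56 / 2.0 = 28.
- Weeks = fractions / 5. IIIA: 25 / 5 = 5.0. IIIB: 28 / 5 = 5.6.
- Weekly doses: about 5 in IIIA and about 6 in IIIB. A midweek start could add one.

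A limit of 1 or 2 doses would then end early in the weekly course. In TPF, which Section 5.2 gives for 3 cycles, the same clause behaves differently. If each cycle carries one cisplatin dose, after dose 1 or 2 is every point at which a later cycle remains, so the clause restricts nothing. One sentence thus serves two regimens in which it has different effects.

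**Audiometry.** Section 7.2.1 requires a test at baseline and before each dose. The two calendars show none.

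**The case against.** The strongest defence is that these rules are mostly permissive and can be read together. Both hearing paragraphs say that carboplatin may be used. The one with the dose clause does not forbid a later switch; it is silent, and the other supplies the rule. The two agree for grade 3 after one or two doses. Stopping cisplatin and replacing it with carboplatin are also compatible. For neuropathy, one rule governs leaving cisplatin and the other stopping carboplatin; the latter directly follows text on carboplatin dose reduction, so they can be taken in sequence. This stands as far as it goes: the hearing paragraphs overlap incompletely rather than oppose each other, and the neuropathy conflict is confined to grade 3 and above. It does not remove the mismatch in grade, the unclear dose clause, or the patient first graded at 3.

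Four stronger readings are tempting and are not supported.

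- *Most of the course gets contradictory hearing rules.* A reader might take 3 of 5 doses (60%) or 4 of 6 (67%) as lying outside the window. After the final dose there is no cisplatin left to replace, so the decision points outside it would be 2 of 4 (50%) or 3 of 5 (60%). Even these rest on an unstated dose count and on applying the clause to hearing. The documents give no timing of onset, so none is a share of patients or events.
- *Patients will never be tested.* Section 7.2.1 still requires audiometry. The calendar gap creates a risk of omission and does not cancel the requirement.
- *The standard-of-care entry for blood tests contradicts the dose tables.* It does not. The Thrombocytopenia paragraph sets pre-chemotherapy thresholds and Section 7.2.2 gives its own timing for counts and creatinine. A cross-reference would help, no more.
- *Late vomiting is unmanaged.* Antiemetics are required in Section 5.1 and unacceptable toxicity is a removal criterion in Section 6.2. What is missing, if the clause applies to vomiting, is a provision for substitution after the second dose.

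**Conclusion.** The point holds as three internal inconsistencies.

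1. The neuropathy rules collide at grade 3 and above, and only there.
2. The two hearing paragraphs differ on grade (3 or 4 against 3 only) and possibly on timing. The scope of the dose clause is unclear, as is its application to a weekly schedule of about 5 to 6 doses on the stated assumption.
3. Audiometry is mandatory in Section 7.2.1 and absent from both calendars.

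The number of patients affected cannot be estimated from the documents. Any understatement of the hearing-loss rate depends on sites following the calendar and missing the text. The point bears on on-treatment management in Groups IIIA and IIIB, on salvage that uses cisplatin, and on the toxicity endpoint. It has no bearing on the Group I sample size of 100 or its precision. Which rule is clinically right is not a question this review answers.

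**What to change.** Reconcile the Peripheral Neuropathy paragraph with the Neurotoxicity paragraph, and the Ototoxicity paragraph with the Ototoxicity, Nausea and Vomiting paragraph. The sponsor's clinicians decide which rule governs in each pair. The revised text should make plain which grades each rule covers, which toxicities the dose clause limits, and how it applies to weekly chemoradiotherapy and to TPF.

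Make the Section 10 calendar and the audiometry requirement in Section 7.2.1 agree. If the requirement stands as written, that means one added row for the chemoradiotherapy groups. In the same edit, the standard-of-care entry for blood tests could cross-refer to the thresholds and timing already in Sections 7.2.1 and 7.2.2.

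The cost is a short amendment to one dose section and the calendar. No test is added beyond those Section 7.2 already requires. The downside is that sites that have followed the calendar will have to perform audiometry that the protocol already asks of them.

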### Neurotoxicity

- In the event of neurotoxicity ( $\geq$  grade 3), Carboplatin therapy is discontinued.

### Nephrotoxicity

If, despite adequate rehydration, serum creatinine increases to Formula to calculate Creatinine Clearance:

$$\text{CrCl (mL/min)} = \frac{(140-\text{age}) (\text{weight kg})}{72 \times \text{serum creatinine (mg/dL)}}$$

N.B. for females, use 85% of calculated CrCl value.

- Grade 0, 1: No change
- Grade  $\geq 2$ : Carboplatin at an AUC of 2.0 may be substituted for Cisplatin

#### 7.2.2 Carboplatin (AUC 2.0)

The carboplatin dose for weekly concurrent chemoradiotherapy is an AUC of 2.0. Thereafter, the AUC will be changed only in case of hematological toxicity.

See the tables below for approach to myelosuppression.

**Table: Carboplatin dose modification based on ANC**

ANC ( $\times 10^9/\text{L}$ ) within 24 hrs. of therapy	Action to be taken
$\geq 1.5$	Treat at current dose
$\geq 1.0, < 1.5$ $< 1.0$	Treat at AUC of 1.5 Hold treatment, and resume therapy at AUC of 1.5 at the next weekly therapy planned when ANC $\geq 1.0$ . If neutropenia requiring further

CONFIDENTIAL

This document is confidential. Do not disclose or use except as authorized.

chemotherapy break occurs, carboplatin will be discontinued for the remainder of the therapy.

\*\*For febrile neutropenia, instructions for ANC <1.0 will be followed. In addition, prophylactic antibiotics and growth factor support may be administered as clinically indicated.

**Table: Carboplatin dose modification based on platelet count**

Platelet count within 24 hrs. of therapy	Action to be taken
≥ 100,000	Treat at current dose
< 100,000	Hold treatment, and resume therapy at AUC of 1.0 at the next weekly therapy planned when platelets ≥ 100,000. If thrombocytopenia requiring further chemotherapy break occurs, carboplatin will be discontinued for the remainder of the therapy.

- Renal toxicity: Serum creatinine will be measured weekly within 24 hours of carboplatin dosing. If the serum creatinine has not changed more than 25% relative to the serum creatinine at baseline, the creatinine clearance and carboplatin dose need not to be recalculated. If there is a rise or fall greater than 25% relative to baseline serum creatinine values, then the creatinine clearance and carboplatin dose must be recalculated.

## 8.0 DRUG FORMULATION AND ADMINISTRATION

Drug formulation and administration are in accordance with commercially available product guidelines for all agents listed in Section 5.0.

## 9.0 CORRELATIVE/SPECIAL STUDIES

### 9.1 Probable Laboratory Correlative Studies

This clinical trial aims to investigate a reduction in radiation intensity in patients with HPVOC. The goals of these exploratory translational studies are to understand the tumor biology, immunology, and epidemiology; and to develop predictive biomarkers to be examined in a larger prospectively randomized trial.

The following projects will be carried out with specimens from study participants:

- Tumor tissue will be evaluated for the following markers (this is a preliminary list which may change and expand as new technology and biomarkers become available: HPV copy number, c-Met expression, BCL-x, EGFr copy number, EGFr expression and EGFr phosphorylation.
- CTC assessment: The number of circulating tumor cells will be evaluated as a possible prognostic indicator.
- Cytokine profiling of the patients plasma will be assessed with baseline samples obtained prior to therapy.
- Circulating immune cells will be assessed including MDSC, T regulatory and T cell subsets.

CONFIDENTIAL

This document is confidential. Do not disclose or use except as authorized.

5. The immunologic function and specificity of patient's T lymphocyte responses to HPV epitopes will be studied and targeted epitopes identified.
6. Serologic responses to HPV proteins will be investigated in patients over time in response to therapy.
7. Tissue microarrays and IHC will be used to establish differences between primary tumors with and without distant spread.

## 9.2 Specific Study Plans

The following studies are given a brief description as technology will change and samples will not be accessed until the study is complete.

### 2) Serologic assessments

We have developed a novel multiplex antibody assay using the Luminex system that allows us to establish the titers of complex and seemingly heterogeneous antibody responses to the full genome of HPV16. Using this system we will monitor the antibody response of the HPVOC prior to, and 6 months after therapy has completed and then at 12 months and then at 24 Months and 36 months to determine if response can predict tumor control, and can establish patterns that might be useful in predicting the development of cancers.

### 3) Tissue microarrays

There will be distinct differences between primary tumors and metastatic, nodal and persistent disease in patients. We will use TMA to evaluate biomarkers and tumor differences that can be used to predict metastatic behavior and response. While tumor control is frequently a process related to tumor volume, those cells that can metastasize may have a distinct signature that can point to a pathway that can be exploited for better anti-tumor therapy, could be identified in small numbers of tumor cells, might be present in CTC, etc. This is exploratory study data set.

## 9.3 Blood and Tissue Collection and Preparation

Blood will be collected to measure plasma and serum factors such as antibodies, cytokines, DNA, etc. and cells for immune studies and germ line DNA. The target amount to be collected from each subject will be less than 200 mls of whole blood (46ml at baseline, 3 month (or pre-XRT) and 24 months; 16 ml at 6, 12, and 36 months). Blood will be collected in 1x 6ml red top tube and 4 x 10ml green top tubes at baseline, 3 month (or pre-XRT) and at the 24 month visit. Only 1 red top tube and one green top tube will be collected at the 6 month, 12 month, and 36 month visits. Processing and labeling of

CONFIDENTIAL

This document is confidential. Do not disclose or use except as authorized.

the blood will be done according to the “Blood Handling” section outlined below. Lag time between collection and the start of processing will be within 5 hours and this time will be recorded for each sample. Components will be stored from these tubes including serum, plasma and buffy coat. If collected and handled properly, each of the tubes should yield approximately 3mls of serum. Serum will be maintained as 1ml aliquots and frozen and stored at -80°C and buffy coat will be stored from green tubes, at local institutional temperature guidelines. A portion of each of these samples will be stored at the biospecimen repository, and a portion maintained at this facility, until exhausted. Samples will be labeled a code linked to the patient case report form. All patients will have tumor testing for HPV and p16 in a central laboratory as part of their screening. Slides and microarrays from tumor tissues will be labeled similarly as blood samples above.

### **Blood Handling**

Blood collection will be performed before surgery (if necessary) and in the absence of any systemic anesthesia.

Samples (6 ml of blood/tube) will be obtained at each visit as noted, according to the table below for Group 1. Times refer to post-surgery collection. For Group 2 and 3 there will be a pre-radiation sample in place of the 3 month post-surgery collection.

	Pre-Surgery	Post-Surgery				
	Baseline	3 ± 1 Month Or preXRT 	6 ± 1 Month	12 ± 1 Month	24 ± 2 Month	36 ± 2 Month
	V1	V2	V3	V4	V5	V6
Serum (red tops)	X	X	X	X	X	X
WBC (green tops)	xxxx	xxxx	X	X	xxxx	X

 pre-XRT for Groups 2 and 3

Viable lymphocytes will be processed from green top tubes using standard ficoll-hypaque density gradient separation. Buffy coat layers will be stored as viable cells in DMSO-containing media at -80C to -170C.

Blood for serum will be spun within 5 hours of collection. Blood tubes will be spun at 3000 x g for 10' at 4°C and the serum removed by pipetting. Serum will be stored in 1ml aliquots. All samples will be stored at -80°C. White blood cell fraction will be stored in a single tube at local institutional temperature guidelines and kept locally.

### **Tissue Collection**

All patients will have their tumors tested for HPV and p16 in the central laboratory at Icahn School of Medicine at Mount Sinai per current standard protocol. Paraffin embedded and formalin fixed blocks from the original and subsequent biopsy specimens will be sent to the laboratory and will be cut in his laboratory for PCR testing and IHC. The primary untreated tumor will be tested for HPV and p16 prior to the start of radiotherapy or concurrent chemoradiotherapy.

Additional slides, from 5-20, and tissue microarrays will be cut from the blocks and stored in the Mount Sinai Biorepository before they are returned to the site. Any additional biopsies from the primary tumor or a recurrence will be obtained and handled in the same fashion.

CONFIDENTIAL

This document is confidential. Do not disclose or use except as authorized.

